Ongoing analysis of our cohort data provides evidence that the proposed study is highly relevant to the MPHIC patient population, as age- and BMI-adjusted percent density of the breast tissue was found to be similar between Latinas at MPHIC and non-Hispanic whites in a long-standing Mayo Clinic patient cohort, thus Latinas and non-Hispanic whites appear to share a major independent risk factor for breast cancer. Furthermore, we conducted brief assessments of English language proficiency, health literacy, and awareness of breast density for some of the MPMSS participants and our data show that the MPHIC screening mammography population reflects an important target group for educational interventions in the context of new density legislation. Specifically, our data reveal limited English proficiency: the percentage of women indicating "not too well" or "not at all" for understanding spoken English was 75%, for speaking English, 77%, and for reading English, was 72%. With regard to health literacy, 47% of women were "somewhat confident" or less that they could fill out medical forms by themselves. Importantly, only 8% of women indicated that they had heard of the term 'breast density.' Eighty-seven percent of women who enrolled in the cohort during the first 6 months of recruitment reported receiving their previous mammogram at MPHIC. These preliminary data will guide our understanding of the needs of the population with regard to presenting educational information about breast density and provides evidence that the MPHIC mammography screening population is a relatively stable one, and that longitudinal research is feasible.

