All consented patients will be asked to complete a baseline (T1) survey [Attachment 6] that includes: demographic characteristics; breast density risk factors (parity, age at menarche, menopausal status, hormonal contraceptive use, breastfeeding, and age at first birth); Family history of breast cancer; and mammography screening history (approximate lifetime number of mammograms, number of times recalled, number of breast biopsies). The primary outcome measure for Aim 1 is anxiety. Anxiety will be measured using the state anxiety subscale of the State-Trait Anxiety Inventory (STAI). This measure was selected because of its known psychometric properties, its use in the mammography literature, and our own experience with its use in an intervention study involving Latinas attending cancer screening. Additional psychosocial measures will include health literacy, cancer fatalism, self-efficacy to return for mammography at the next screening interval, breast cancer worry, perceived risk of breast cancer using numerical, verbal and comparative estimates, and the Patient-Reported Outcomes Measurement Information System (PROMIS) measure (short form) addressing depressive symptoms. Knowledge will be assessed using two previously developed items for the national survey regarding density as an independent risk factor and as having a masking effect as well as additional items derived from the written education materials. Our selection of short form assessments where available carefully balances capturing a comprehensive set of important psychosocial measures while reducing respondent burden. We have chosen published measures with favorable psychometric properties and use existing measures where available. Administering the depression measure from the PROMIS Initiative (www.nihpromis.org) will utilize an important resource for validated patient-reported outcomes (PROs) and position our study results within a larger, cross-institute NIH initiative. Based on our experience at MPHC, an interviewer-facilitated mode of survey completion is preferred by patients over self-administered surveys and results in higher quality data. We will provide paper surveys in English and Spanish; participants can mark their own answers or follow along and mark their answers as questions are read to them by the CRC. We anticipate the study assessments will take approximately 30 minutes to complete. The study coordinator will review the responses to the PROMIS items related to depression following completion of the T1 survey. Based on the responses, the study coordinator will follow the steps in the Plan for Depression Questions [Attachment 18]. If the plan

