Follow-up (T2) Assessment. Participants will be contacted by study staff using Mayo Clinic or Mountain Park telephone that will display the Mountain Park phone number.[Attachment 8] approximately 2 weeks after patients have their mammogram to complete a follow-up survey [Attachment 9]. If the study staff is unsuccessful in reaching the participant by telephone, the T2 survey will be mailed to the participant with a cover letter [Attachment 10] and return postage-paid envelope. If the patient has not actively refused or withdrawn, or completed the T2 assessment, study staff will attempt to follow-up by telephone. Study staff may also send a certified letter asking the participant to call them and schedule a time to complete the survey (see Attached reminder letter). If telephone and mail contacts are not successful, participants will be coded in RAVE as a non-responder at T2. The CRC will collect the data over the telephone and mark the answers on a paper survey for double data entry by the Survey Research Center (SRC). The CRC will ask questions designed to measure acceptability of the method by which women received their breast density results and satisfaction with the content and clarity. Knowledge will be re-assessed using the same items described in the baseline assessment. Women will be queried about their own breast density as a check that the mailed notification was read and processed. Anxiety, depressive symptoms, perceived risk of breast cancer, self-efficacy, and breast cancer worry measures administered at baseline will be repeated. Behavioral intention to return for a screening mammogram at the recommended interval will also be assessed. All women will be asked if they discussed their breast density with their health care provider. Women with dense breasts will be asked if they discussed supplemental screening options with their health care provider (e.g., breast ultrasound, MRI). Questions will address whether each of these activities occurred, and if not, whether they are pending (requested by the patient). If not requested, intentions regarding these behaviors will be measured. The study coordinator will review the responses to the PROMIS items related to depression following completion of the T2 survey. Based on the responses, the study coordinator will follow the steps in the Plan for Depression Questions [Attachment 18]. If the plan calls for study personnel to contact the patient, she will do so in accordance with the Plan for Depression Questions and using the Script for Depression Questions Follow-up [Attachment 19].

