
Follow-up (T3) Assessment. Participants will be contacted by study staff using Mayo Clinic or Mountain Park telephone that will display the Mountain Park phone number.[Attachment 11] approximately 1 year after patients have received their mammogram results to complete the third survey [Attachment 12]. Reminder calls and a T3 survey mailing with cover letter [Attachment 13] will follow the procedures outlined for the T2 assessment. Study staff may also send a certified letter asking the participant to call them and schedule a time to complete the survey (see Attached reminder letter). Study staff may also approach patients in clinic if they present to the mammography unit for screening.. If telephone, in-person and mail contacts are not successful, participants will be coded in RAVE as a non-responder at T3. The T3 assessment will include repeated measurement of anxiety, depressive symptoms, breast cancer worry, perceived risk, and discussion of their breast density with their health care provider. It will include questions regarding information seeking about the topic of breast density and re-assess breast density knowledge. Intentions regarding future utilization of mammography and supplemental breast screening will be measured. Attendance at mammography will be queried to capture self-reported screening behavior that may have occurred elsewhere and would not be documented in the MPHC EMR; however this is unlikely because many patients receive low-cost mammography through special programs at MPHC. All women will be queried at the T3 assessment about their attendance at mammography; these self-report data

will be corroborated with EMR data. Women who indicate they received a mammogram elsewhere will be asked where and when this occurred. The study coordinator will review the responses to the PROMIS items related to depression following completion of the T3 survey. Based on the responses, the study coordinator will follow the steps in the Plan for Depression Questions [Attachment 18]. If the plan calls for study personnel to contact the patient, she will do so in accordance with the Plan for Depression Questions and using the Script for Depression Questions Follow-up [Attachment 19].

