Subject ID, subject code or any other person-specific unique identifying number, characteristic or code that can link the subject to their medical data		
Dates: All elements of dates [month, day, and year] directly related to an individual, their birth date, date of death, date of diagnosis, etc. Note: Recording a year only is not a unique identifier.		
Social Security number		
Medical device identifiers and serial numbers		
Biometric identifiers, including finger and voice prints, full face photographic images and any comparable images		
Web Universal Resource Locators (URLs), Internet Protocol (IP) address numbers, email address		

Street address, city, county, precinct, zip code, and their equivalent geocodes	X	X
Phone or fax numbers	X	X
Account, member, certificate or professional license numbers, health beneficiary numbers		
Vehicle identifiers and serial numbers, including license plate numbers		
Check 'None' when none of the identifiers listed above will be recorded, maintained, or shared during the conduct of this study. (exempt category 4)	 None	 None

In all cases, "External" refers to our trained study team members at MPH. Information will not be shared with any other External entities.

Data Analysis

Power analyses and study endpoints are not required for minimal risk research, pilot or feasibility studies.

No statistical information. *If checked, please explain:*

Power Statement:

A total of 2,000 Latinas will complete baseline assessments and be randomized to one of three groups of breast density notification: usual care, enhanced, or interpersonal approaches (approximately 667 women per group) (see Figure 1). Applying a 10% attrition rate between enrollment and the first follow-up time point and an additional 20% after one year, we have planned for a sample size of 1,800 (2,000*0.90, 600 per group) for T2 measures and a sample size of 1,400 (2,000*0.70, 466 per group) for T3 measures.

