Aim 1 will compare the percent change in anxiety (STAI) from baseline between the three study groups at one month (T1) and 1 year (T3) following notification. Assuming the percent change may likely range from -100% to +100% (range of 200 percentage points), we conservatively assume a standard deviation of 50 percentage points (range/4) in the percent change measure. We will have 80% power (along with 1.7% type-I error rate) to detect a difference of 9.3 in average percent change between any two of the groups with a two-sample t-test at T2 with 600 per group. At T3, we will have 80% power to detect a difference of 10.6 (466 per group).

The second outcome will be knowledge regarding breast density, measured ordinally as the number correct of 3 key items (range 0-3 correct). This will be tested with pairwise Wilcoxon rank-sum tests, for which the null hypothesis is that the probability of someone answering more items correctly in one group versus another is 0.5 (i.e. equal chance). At T2, with 600 women per group, we will have 80% power (along with 1.7% type-I error rate) to detect a probability of 0.554 or more between any two of the groups. At T3, we will have 80% power to detect a probability of 0.561 (466 per group).

Aim 2 will compare adherence to next routine screening mammogram between the three notification groups. This outcome "adherence to next annual screening" is pertinent to all 2,000 women and will be obtained via EMR. A sample size of 666 in each group will yield 80% power to detect a difference of 9 percentage points between any two of the groups (type-I error rate 1.7%) based on a chi-square test.

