Aim 3 will qualitatively analyze documentation provided by the *promotora* after each patient interaction in the interpersonal study group. Based on the recommendation of Morse,¹¹⁹ we will have ample data from over 600 patient-*promotora* interactions to capture a range of responses. Furthermore, this large sample size will offer the opportunity to qualitatively examine the type of information exchanged for particular subgroups of patients, such as Spanish-speaking only, those receiving notification that they have dense breasts, and those receiving notification that they do NOT have dense breasts. The analysis of Aim 3 qualitative data will provide a rich resource for informing the design of targeted educational materials for specific populations and developing generalizable tools to enhance communication about appropriate risk-based screening for breast cancer.

Data Analysis Plan:

Analytic Approach for Specific Aim 1

This Aim will compare anxiety as well as knowledge gained between breast density notification approaches (usual care, enhanced, interpersonal). Anxiety will be measured using the state anxiety scale within the State Trait Anxiety Inventory (STAI). Items within this scale are rated on a 0 to 3 Likert-type scale and scores are calculated as the sum of the items. The possible scores can range from 0-60, with higher scores indicative of greater anxiety. To adjust for baseline anxiety levels, we will calculate the percent change in anxiety from baseline at each follow-up: $100 * (\text{follow-up anxiety} - \text{baseline anxiety}) / \text{baseline anxiety}$. We hypothesize that there will be less increase in anxiety for the interpersonal group as compared to the enhanced or usual care groups. The percent change will be compared between the three notification study groups with pairwise t-tests at one month as well as at one year following notification. To account for three pairwise comparisons within each time point, P-values less than 0.017 will be considered statistically significant, to preserve an overall type-I error rate of 0.05 within each time point.

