Knowledge regarding breast density will be measured as the number of statements answered correctly as previously described. The number of items answered correctly (range of 0-3) will be compared between the three notification groups with pairwise Wilcoxon-rank-sum tests at one month as well as at 1 year following notification. We assume that baseline knowledge will be similar between the groups due to randomization, and we hypothesize that knowledge will be greater in the interpersonal group as compared to the enhanced or usual care groups. To account for three pairwise comparisons within each time point, P-values less than 0.017 will be considered statistically significant, to preserve an overall type-I error rate of 0.05 within each time point.

Analytic Approach for Specific Aim 2

This Aim will compare adherence to next routine screening mammogram between breast density notification approaches (usual care, enhanced, interpersonal). This information will be obtained from the EMR. The percentage of women who adhere to their next routine screening mammogram will be compared between the three notification groups with pairwise chi-square tests. We hypothesize that women randomized to the interpersonal group will be more likely to adhere to next screening mammogram relative to either the usual care or enhanced study groups. To account for three pairwise comparisons P-values less than 0.017 will be considered statistically significant to preserve an overall type-I error rate of 0.05

Analytic Approach for Specific Aim 3

Framework analysis will be used to understand and analyze the qualitative data provided by the *promotora*. This approach is based in content analysis and allows for *a priori* themes to be identified and categorized as well as *de novo* themes that emerge through inductive analysis. The process begins with familiarization in which the content and range of responses is examined. Next, a thematic framework is generated by identifying key issues, concepts, and themes which will be used to reference the data. We anticipate that issues regarding understanding MBD, supplemental breast screening, and breast cancer risk will arise in the data, but emerging issues will also be captured. Finally, the analytic framework will be applied

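### The knowledge analysis does not use the T1 knowledge score already collected: some precision is lost, and baseline imbalance among women retained at T2 and T3 goes unadjusted

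*Combined protocol and SAP*

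**What the plan says.** The combined protocol and SAP collects knowledge at three times. The Methods text on the baseline survey states "Knowledge will be assessed using two previously developed items for the national survey", together with further items drawn from the educational materials. The T2 section states "Knowledge will be re-assessed using the same items described in the baseline assessment". The T3 section says the survey will "re-assess breast density knowledge", without saying whether the items are identical.

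In the Data Analysis Plan (Specific Aim 1), the 0 to 3 follow-up score is compared between groups by pairwise Wilcoxon rank-sum tests at each follow-up, with P below 0.017 as the threshold. Baseline enters only as an assumption: "We assume that baseline knowledge will be similar between the groups due to randomization". No adjusted or sensitivity analysis is given for knowledge.

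For anxiety, the same section does use the baseline: "To adjust for baseline anxiety levels, we will calculate the percent change in anxiety from baseline at each follow-up".

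The Power Statement plans for loss: "Applying a 10% attrition rate between enrollment and the first follow-up time point and an additional 20% after one year". That leaves 600 women per group at T2 and 466 at T3, out of about 667 randomized.

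**The concern.** A baseline measure of the same outcome is usually the most useful covariate a trial has, and this one is already in the database. Leaving it out has two consequences.

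- **Precision.** Variation in follow-up knowledge that T1 knowledge could explain stays in the error term.
- **Retention.** The appeal to randomization covers everyone enrolled. The tests use the women who respond. Only the interpersonal arm speaks with a *promotora*, and that contact could change who stays in the study. If retention then depends on T1 knowledge differently by arm, the retained groups start from different levels and the planned test does not correct for it. This matters most at T3, where 30% are expected to be lost.

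Aim 1 is worded in terms of knowledge gain. That alone is no fault: with randomization and complete follow-up, the expected difference in follow-up scores equals the expected difference in gain. The equivalence weakens once the groups analysed are subsets.

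**Working it through.** **1. The plan's own figures.** Inputs from the Power Statement: 80% power, 1.7% type I error, 600 and 466 per group. Noether's formula without ties, two-sided, is P = 0.5 + (z₁₋α/₂ + z_power)/√(6n), with 2.387 + 0.842 = 3.228 (unrounded sum).

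- T2: 0.5 + 3.228/√3600 = 0.5538 (stated 0.554).
- T3: 0.5 + 3.228/√2796 = 0.5611 (stated 0.561).

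Both reproduce, so the power statement is correct for the unadjusted test. Allowing for ties would lower both values, so they are conservative.

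**2. Precision gained at T2.** The documents give neither the T1 score distribution nor its correlation with follow-up, so both are assumed. Two T1 distributions over scores 0, 1, 2, 3 were used:

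- (0.92, 0.05, 0.02, 0.01), guided by the Background figure that "only 8% of women indicated that they had heard of the term" for breast density;
- (0.68, 0.14, 0.10, 0.08), a milder floor.

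A latent bivariate normal was cut to four levels, with 600 per group, two-sided 0.017 and 2,000 trials per setting (Monte Carlo error about 1 point). Follow-up scores were uniform or (0.68, 0.14, 0.10, 0.08), with an effect giving unadjusted power of 79-81%. The adjusted ranges cover the stratified Wilcoxon test and the proportional-odds model with T1 as covariate.

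| Scoring 0 at T1 | Latent correlation | Rank correlation | Adjusted power |
|---|---|---|---|
| 92% | 0.3 | 0.15 | 80-82% |
| 92% | 0.5 | 0.25-0.26 | 82-84% |
| 68% | 0.3 | 0.21-0.22 | 81-82% |
| 68% | 0.5 | 0.36-0.38 | 85-87% |

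A linear approximation agrees: power = Φ(3.228/√(1−r²) − 2.387). For r = 0.2 this is Φ(3.295 − 2.387) = 82%; for r = 0.3 it is Φ(3.384 − 2.387) = 84%.

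**3. Retention at T3.** Setting: 667 per arm, no true effect, 30% lost in each arm, 68% scoring 0 at T1, uniform follow-up, 12,000 trials. One arm retains 70% regardless of T1 score. The other retains women scoring 1 or more better than women scoring 0:

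- 10-point gap: 0.68 × 0.668 + 0.32 × 0.768 = 0.70. The share scoring 1 or more among those retained is 0.246/0.70 = 35%, against 32% in the other arm.
- 20-point gap: 0.68 × 0.636 + 0.32 × 0.836 = 0.70. That share is 0.268/0.70 = 38%, against 32%.

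| Latent correlation | Gap | Unadjusted error rate |
|---|---|---|
| 0.3 | 10 points | 1.8% |
| 0.3 | 20 points | 2.5% |
| 0.5 | 10 points | 2.3% |
| 0.5 | 20 points | 5.2% |

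Stratified by T1 score, the error rate is 1.6-1.9% throughout. With no gap the unadjusted rate is 1.7%. Further simulations of the last row gave 4.7-5.1% unadjusted. With 92% scoring 0, a 20-point gap gives 1.9-2.2% (normal approximation).

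**4. Retention at T2.** With 10% loss a 20-point gap is impossible: at 68% scoring 0, retention of women scoring 1 or more would be 0.90 + 0.68 × 0.20 = 104%. A 10-point gap gives 1.9-2.3% (68% scoring 0) or 1.7-1.8% (92% scoring 0), by normal approximation. The retention argument therefore carries little weight at T2.

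**The case against.** The planned test is standard, valid and prespecified, and knowledge is the second outcome of Aim 1, after anxiety. In the scenario closest to the clinic's own data (92% at zero) the power gain is at most a few points, close to simulation error. The 68% scenario has no source as a clinic score distribution. The 5.2% needs four assumptions at once: 68% at zero, latent correlation 0.5, a 20-point gap, and that gap in one arm only. The documents report no differential retention. All of this stands, and it limits the size of the point.

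The strongest objection concerns what the adjustment can do. The simulation in the working makes dropout depend only on the T1 score, so stratifying on T1 has to work. If retention in one arm depends instead on knowledge at follow-up, the result differs. For scores of 2 or 3 against 0 or 1, with the other T3 settings unchanged, a 10-point gap gives an error rate of about 8% unadjusted and 7% stratified. A 20-point gap gives about 33% and 26-30%. This also stands: adjustment removes only the imbalance that T1 knowledge explains and does not cure informative dropout.

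Finally, a proportional-odds model reports a conditional odds ratio, not the probability scale used in the Power Statement. That is a fair caution about which model to choose, not a reason to ignore T1.

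None of this defends leaving out the covariate. The only reason the plan gives is balance by randomization, which does not extend to the retained subset.

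**Conclusion.** The concern holds. The T1 knowledge score is collected, the knowledge analysis does not use it, and anxiety in the same aim is treated differently. This is an efficiency and robustness point, not a validity error.

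The likely power gain is small: 0-4 points over 80% if almost all women score 0 at T1, and up to about 7 points under a milder floor with latent correlation 0.5. The protection at T3 ranges from negligible to keeping a 5.2% error rate near 1.7%. It applies only if loss depends on baseline knowledge differently by arm. Confidence is high for the omission. The magnitudes rest on an assumed T1 distribution, correlation and retention pattern.

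**What to change.** In the Data Analysis Plan for Specific Aim 1, before results are seen:

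- Analyse T2 and T3 knowledge with one named method: a Wilcoxon test stratified by T1 score, or a proportional-odds model on study group with the T1 score as covariate. The stratified test stays closer to the scale of the power calculation.
- Score T1 on the same three key items used at T2. That score can serve as the covariate at T3 even if the T3 items differ.
- Keep the three pairwise contrasts and the 0.017 threshold. Keep the unadjusted Wilcoxon test as a sensitivity analysis, and note that 0.554 and 0.561 refer to that test.
- Tabulate T1 knowledge by group among T2 and T3 responders, and say that the adjustment does not address dropout related to later knowledge.

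The cost is analysis-plan wording and a little analysis time: no new items, visits or participants. The proportional-odds assumption would need checking, and sparse T1 levels may need merging for the stratified test.

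### Aim 2: the unadjusted chi-square is valid and adequately powered, but a pre-specified covariate-adjusted risk difference could add precision from T1 data already collected

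*Combined protocol and SAP*

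**What the plan says.** The Data Analysis Plan (Analytic Approach for Specific Aim 2) takes adherence from the EMR and states that the percentages "will be compared between the three notification groups with pairwise chi-square tests". The threshold follows: "To account for three pairwise comparisons P-values less than 0.017 will be considered statistically significant to preserve an overall type-I error rate of 0.05". No adjusted model and no sensitivity analysis is given for this aim.

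The Power Statement rests on the same test: "A sample size of 666 in each group will yield 80% power to detect a difference of 9 percentage points". It treats the outcome as complete, saying that it "is pertinent to all 2,000 women and will be obtained via EMR". Allocation is to "usual care, enhanced, or interpersonal approaches (approximately 667 women per group"; no stratification factor is named.

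The T1 survey, described under Study Design and Methods, collects demographics, "mammography screening history (approximate lifetime number of mammograms, number of times recalled, number of breast biopsies" and, among the psychosocial measures, "self-efficacy to return for mammography at the next screening interval". None of these has a role in the Aim 2 analysis. Elsewhere the plan does use baseline information: Aim 1 works with percent change from baseline anxiety, and Exploratory Aims 2 and 3 use regression with adjustment for confounders.

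**The concern.** How often a woman has been screened, whether she has been recalled or biopsied, and how confident she is about returning are natural candidates for predicting whether she returns. If they do predict return, a comparison on arm alone has a larger standard error than the collected data would allow. The choice matters most for Aim 2 because it is the only behavioural outcome with a stated test and power calculation. Naming covariates in advance also closes off post hoc selection should a baseline imbalance appear.

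**Working it through.** **Inputs.** 666 women per group, 80% power, 9 points and type-I error 1.7% come from the Power Statement; 0.017 per pair comes from the Aim 2 analysis section. Assumed: two-sided testing (sidedness is not stated) and return rates near 50%, where the variance is largest (no rate is given).

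**Step 1: the plan's own figure.** Pooled two-proportion formula, 45.5% versus 54.5%:

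n = [2.3867 × √(2 × 0.5 × 0.5) + 0.8416 × √(0.455 × 0.545 + 0.545 × 0.455)]² / 0.09² = 642 per group, or 665 with continuity correction.

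With 666 per group, power at 9 points is 81.6%. The stated figure holds without adjustment. At higher rates there is more room: from a 70% base rate the detectable difference is 7.8 points and power at 9 points is 91.8%.

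**Step 2: effect of adjustment.** Let R² be the share of the yes/no outcome's variance explained by the covariates. The documents give no value, so a range is shown.

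- Unadjusted detectable difference: 3.2283 × √(2 × 0.25 / 666) = 8.85 points, where 3.2283 = 2.3867 + 0.8416.
- Adjusted: 8.85 × √(1 − R²).
- Power at 8.85 points: Φ(3.2283 / √(1 − R²) − 2.3867).
- Equivalent unadjusted size per group: 666 / (1 − R²).

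| Assumed R² | Detectable difference (points) | Power at 8.85 points | Equivalent n per group |
|---|---|---|---|
| 0 | 8.85 | 80% | 666 |
| 0.015 | 8.78 | 80.7% | 676 |
| 0.056 | 8.59 | 82.5% | 705 |
| 0.112 | 8.34 | 85.1% | 750 |
| 0.174 | 8.04 | 87.8% | 806 |

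The last three rows correspond to a logistic covariate score with SD 0.5, 0.75 and 1.0 (AUC 0.636, 0.691 and 0.739).

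**Step 3: simulation.** 4,000 replicates per scenario, 666 per group, 45.5% versus 54.5%, chi-square against a linear model with robust standard error. This is a simpler estimator than the one recommended under the fix, but it targets the same risk difference. Power was 80.7% v 80.7% at R² = 0, 81.3% v 83.6% at 0.05, 81.3% v 86.3% at 0.10 and 80.9% v 89.8% at 0.20. Type-I error was 1.5% to 1.8% for both analyses.

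**Step 4: size of chance imbalance.** For a binary predictor with 50% prevalence, the between-arm difference has SD √(2 × 0.25 / 666) = 2.74 points, so 95% of differences lie within 1.96 × 2.74 = 5.37 points. If the predictor shifts adherence by 10 to 30 points, an imbalance at that limit moves the estimate by 5.37 × 0.10 = 0.54 to 5.37 × 0.30 = 1.61 points. The standard error of the raw difference is 2.74 points.

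**Step 5: cost of dropping women with missing covariates.** At R² = 0.056, losing 5.6% leaves 666 × 0.944 = 629 per group, and 629 / 0.944 = 666. The whole gain is cancelled.

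**The case against.** The strongest objection is that nothing here is wrong. A chi-square between randomized arms is valid and the plan meets its own power target. That stands in full.

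Three stronger readings are tempting and are not supported:

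- A reader might infer that chance imbalance in screening history biases the Aim 2 result. Randomization makes the raw difference unbiased, and its standard error and the 0.017 threshold already allow for such imbalance. Step 4 shows the likely shift is small beside the standard error. Adjustment tightens the realised estimate; it does not repair a bias.
- A reader might infer that the precision comes free. It depends on how well the covariates predict return, which the documents do not show. Every participant is already attending screening, and in the earlier cohort at this centre 87% of early enrollees had their previous mammogram there, so screening history may vary little. At R² = 0.015 the gain is under one power point. Careless handling of missing covariates would lose what is gained.
- A reader might infer that Aim 2 is the only behavioural endpoint. Study Design and Methods also records discussion of density with a provider, delay in follow-up of abnormal mammograms and uptake of supplemental screening. The documents support only the narrower statement made above about a stated test and power.

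A further objection, which also stands, concerns self-efficacy as a covariate. Study Design and Methods places randomization directly after consent and then describes T1; the Power Statement puts baseline assessment before randomization. If a woman knows her arm when she answers, self-efficacy may not be a true baseline value. Age, language and screening history are much less exposed to this.

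**Conclusion.** A cheap improvement, not an error. The Aim 2 chi-square is sound and delivers its stated 9 points at 80% power. Near a 50% return rate, adjustment would lower the detectable difference from 8.85 points to between about 8.6 and 8.0, and raise power at 8.85 points to between about 83% and 88%, if the covariates explain about 5% to 17% of the outcome variance. If they explain nothing, there is no gain, and the loss is negligible with about 1,330 women per comparison. The direction of the effect is secure; its size rests on an R² and a return rate that the documents do not give, and on two-sided testing.

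**What to change.** In Analytic Approach for Specific Aim 2:

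- Make the primary analysis a logistic model of adherence on arm plus a short pre-listed set of T1 covariates: age, survey language, lifetime number of mammograms, and prior recall or biopsy. Average the predictions to an adjusted risk difference for each pair of arms, with a robust standard error, tested at the same 0.017. The result stays in percentage points, so the 9-point planning figure still applies.
- Keep the pairwise chi-square tests as a sensitivity analysis.
- Keep every randomized woman with an EMR outcome by stating a simple missing-covariate rule, for example a missing indicator or single imputation that uses neither arm nor outcome.
- Reconcile Study Design and Methods with the Power Statement on the order of T1 and randomization. Add T1 self-efficacy to return only if T1 is completed before randomization or before the woman knows her arm.

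The cost is SAP wording, one regression with standardization, and the missing-data rule. The T1 survey already collects screening history and demographics, so no new data collection is involved.
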